## 5.5. Multiple Comparisons and Multiplicity

As there is a single primary treatment comparison, no adjustment is required for primary comparisons. No adjustments will be made for multiplicity for other endpoints.

## 5.6. Other Considerations for Data Analyses and Data Handling Conventions

Other considerations for data analyses and data handling conventions are outlined in the appendices:

Section	Component
12.3	Appendix 3: Assessment Windows
12.4	Appendix 4: Study Phases and Treatment Emergent Adverse Events
12.5	Appendix 5: Data Display Standards & Handling Conventions
12.6	Appendix 6: Derived and Transformed Data
12.7	Appendix 7: Reporting Standards for Missing Data
12.8	Appendix 8: Values of Potential Clinical Importance

## **6. STUDY POPULATION ANALYSES**

### **6.1. Overview of Planned Study Population Analyses**

The study population analyses will be based on the Safety Population including GCP non-compliant subjects population (SAFF\_ALL), unless specified to be on the All Subjects Enrolled (ASE) population.

Study population analyses including analyses of subject's disposition, protocol deviations, demographic and baseline characteristics, prior and concomitant medications, and exposure and treatment compliance will be based on GSK Core Data Standards. Details of the planned displays are presented in [Appendix 10: List of Data Displays](#).

### **6.2. Disposition**

The study population summary will use the All Subjects Enrolled (ASE) population and show the number of subjects overall who were enrolled, the number of screen failures and the number with each reason for screen failure. It will also show the number of subjects who were randomised and who were in the modified Intent-to-treat (Loss of Control), modified Intent-to-treat, Safety including GCP non-compliant subjects, and PK populations.

For the Safety including GCP non-compliant subjects, reasons for withdrawal summary will show the number and percentage of subjects who completed the study, who withdrew prematurely from the study and who reported each primary and sub-reason for withdrawal.

### **6.3. Medical Conditions**

The number and percentage of subjects reporting each current medical condition will be presented. This table will include a subheading of 'Cardiovascular Risk Factors,' which will summarise the information taken from the cardiac disorders page in the eCRF. All medical conditions must be summarised on this table regardless of frequency. This will be repeated for past medical conditions.

### **6.4. Concomitant Medications**

Non-Asthma medications will be summarised by Anatomical-Therapeutic-Chemical (ATC) level 1 and ingredient. Asthma medications will be summarised by the latest version of the Respiratory Medication Class (RMC), and will be derived for each asthma concomitant medication. Multi-ingredient medications will be presented according to their combination ATC classification rather than the classifications of the ingredients.

Asthma and non-asthma medications will be listed separately. A listing of the relationship between ATC Level 1, ingredient and verbatim text will be produced for non-asthma medications only.

## 7. EFFICACY ANALYSES

### 7.1. Primary Efficacy Analyses

#### 7.1.1. Endpoint

- Proportion of participants with loss of asthma control over Weeks 0-16
- Proportion of participants with loss of asthma control over Weeks 0-6 (Secondary)

#### 7.1.2. Summary Measure

Bayesian Method (Primary): The posterior probabilities that the ratio of the proportion of subjects with loss of asthma control on GSK3772847 compared with placebo is less than 1.0, 0.75, 0.5 and 0.2 (i.e. a 0%, 25%, 50% and 80% reduction).

Frequentist Method (Supportive): Odds Ratio. The odds of having experienced loss of asthma control on GSK3772847 compared to the odds of having experienced loss of asthma control on placebo.

#### 7.1.3. Population of Interest

The primary efficacy analyses will be based on the modified Intent to Treat (Loss of Control) population, unless otherwise specified.

#### 7.1.4. Strategy for Intercurrent (Post-Randomisation) Events

Intercurrent Event	Primary Estimand	Secondary Estimand
Treatment discontinuation due to AE/SAE (not related to loss of asthma control)	Set to missing.	
 
• If the AE/SAE was deemed related to IP then set as an event (i.e. worst case scenario).
 
• If the AE/SAE was not deemed related to IP then set to missing.
 

Death	Set to missing.	
 
• If the death was deemed related to IP then set as an event (i.e. worst case scenario).
 
• If the death was not deemed related to IP then set to missing.
 

Prohibited/ Concomitant medications that could impact patients' asthma control	Use data as is.	Set as an event (i.e. worst case scenario).
Non-compliance with FP/SAL, FP or study titration	Use data as is.	Set as an event (i.e. worst case scenario).
Continuation in the study after LOC criteria met	Use information from first loss of asthma control.	Use information from first loss of asthma control.

**Note:**

- Identification of whether an event (AE/SAE/Death) is considered related to IP will be identified

- |  |
|--|
| 
using the investigator tick box collected on the eCRF.
 
 
• If the intercurrent event occurs after loss of asthma control then all information on loss of asthma control will be used.
 
• Prohibited/ concomitant medications will be identified as protocol deviations within the prohibited/ concomitant medications category and will have text that start with “LoAC”
 
• Non-compliance FP/SAL, FP or study titration will be identified as compliance <80%, compliance ≥ 120% or not changing from FP/SAL or FP doses according to the predetermined schedule.
 
 |
|--|

If any of the following intercurrent events occurs, then all data will be accepted:

- Pregnancy  
Accidental unblinding

Whilst it’s possible that site staff were unable to administer study drug as they were unable to find a suitable vein, the team felt this would not be caused by the randomised study treatment and the visit would be rescheduled. Therefore, if this occurs all data will be accepted and treated as any other out of window assessment.

### 7.1.5. Statistical Analyses / Methods

Details of the planned displays are provided in [Appendix 10: List of Data Displays](#) and will be based on GSK data standards and statistical principles.

Unless otherwise specified, endpoints / variables defined in Section 7.1.1 will be summarised using descriptive statistics, graphically presented (where appropriate) and listed.

#### 7.1.5.1. Statistical Methodology Specification

Endpoint / Variables

 
• Proportion of participants with loss of asthma control over Weeks 0-16
 
• Proportion of participants with loss of asthma control over Weeks 0-6 (Secondary)
 

Model Specification

 
• The primary endpoint proportion of subjects with loss of asthma control will be analysed for the Modified Intent-to-Treat excluding GCP non-compliant subjects (Loss of Control) population using both Bayesian (primary) and Frequentist (supportive) methods.
 
 
Bayesian Method (Primary):
 
 
• Proc MCMC will be used in order to gain the posterior distribution of the study data combined with a non-information beta(1,1) prior, and screening eosinophil strata included as a covariate. Note: This prior is equivalent to one event on both GSK3772847 and Placebo treatment arms.
 
• Three MCMC chains should be run, with all parameters in the model being assessed for convergence. Each chain will have 10,000 simulations (using a burn-in of 500) and will start with a set seed of 207597 to enable comparison between the main and qc.
 
• The posterior probabilities that the ratio of the proportion of subjects with loss of asthma control on GSK3772847 compared with placebo is less than 1.0, 0.75, 0.5 and 0.2 (i.e. a 0%, 25%, 50% and 80% reduction) will be calculated along with the estimated ratio and associated 95%
 

credible interval. The 95% credible interval will use the highest posterior density where possible, and if this isn't possible then the 2.5% and 97.5% credible intervals will be reported.

- The posterior median and standard deviation will also be reported together with a 95% credible interval.
- In addition to summary tables a plot of the posterior distribution for the ratio of the proportion of subjects with loss of asthma control on GSK3772847 compared with placebo, along with the proportion of subjects with loss of asthma control on GSK3772847 and placebo separately will be generated.
- This analysis will be repeated for loss of asthma control between Weeks 0 and 6.

Frequentist Method (Supportive):

- The proportion of participants with loss of asthma control will be analysed using logistic regression allowing for screening eosinophils strata. It will include fixed effects terms for treatment and screening eosinophil strata.

Fractional Polynomials (Exploratory Analysis for Loss of Control Over Weeks 0-16):

- Screening blood eosinophil count will be transformed using a fractional polynomial term which will be included in the model as a continuous covariate. A treatment group by eosinophil covariate interaction will also be included in the model to allow the magnitude of the interaction (but not the order of the fractional polynomial transformation) to differ with each treatment group). The best fitting model will be selected based on likelihood. The selected best fitting model will be plotted as continuous eosinophil count versus loss of asthma control in each treatment arm. The fit of the model to the raw data will be assessed visually.
- The role of baseline IgE and baseline FeNO (separately) on the effectiveness of GSK3772847 with respect to loss of asthma control will be investigated in a similar way.

### Model Checking & Diagnostics

Bayesian Method (Primary):

- The Markov chain standard error (MCSE) should be compared to the standard deviation of the distribution (SD) to make sure that  $MCSE/SD \leq 0.01$  for all parameters in the mode.
- The Geweke diagnostic test will be used to check whether the mean estimates have converged by comparing means from the early and later part of the Markov chain using a z-score t-test. Large absolute values of the z-score statistic indicate rejection of the null hypothesis of no difference between the mean estimates obtained from the early and latter parts of the chain.
- Gelman & Rubin diagnostic checks should be used to assess if the Markov chains have mixed.
- Visual checks on diagnostic plots will be performed to assess:
  - Has the Markov chain settled down?
  - Are sufficient simulations being run?
  - Is there sufficient burn-in?
  - Is the effective sample size large enough?

Frequentist Method (Supportive):

- None.

### Model Results Presentation

Bayesian Method (Primary):

- The proportions of participants experience loss of asthma control on GSK3772847, Placebo and the ratio of GSK3882747/Placebo will be presented along with their 95% credible interval for all participants combined.

Frequentist Method (Supportive):

- The odds of experiencing loss of asthma control on GSK3772947, Placebo and the odds ratio will be presented along with the 95% confidence intervals and p-value. This will be presented for all participants combined.

Fractional Polynomials (Exploratory Analysis):

- A plot of the relationship between the probability of experiencing loss of control on each treatment as well as the odds ratio versus continuous eosinophils will be produced.

## 7.2. Secondary Efficacy Analyses

### 7.2.1. Endpoint and Summary Measure

Endpoint	Summary Measure

Individual Components of Loss of Asthma Control:
 
 
• Proportion of participants with a <math>\geq 0.5</math> point. ACQ-5 score increase from baseline.
 
• Proportion of participants who have pre-bronchodilator FEV1 decrease from baseline (measured at the end of Run-in) <math>> 7.5\%</math>.
 
• Proportion of participants where inhaled corticosteroids (ICS) cannot be titrated in accordance with the pre-defined schedule.
 
• Proportion of participants who have a significant asthma exacerbation (requiring OCS and/or hospitalisation).
 
• Proportion of participants with a clinically significant asthma exacerbation or inability to titrate ICS according to the pre-defined schedule
 
	
Frequentist Method (Supportive): Odds Ratio.
 
For each endpoint listed, the odds of having experienced loss of asthma control on GSK3772847 compared to the odds of having experienced loss of asthma control on placebo will be produced.

Time to loss of asthma control.
	
Median and lower and upper quartiles (only calculable if <math>\geq 50\%</math>, <math>25\%</math>, <math>75\%</math> subjects lose control for each treatment respectively) for time to loss of asthma control

The incidence, mean rate, and total number per participant of hospitalisations or Emergency Room (ER) visits during the study treatment period.
	
Summary statistics and study treatment exposure (no statistical analysis required).

Responder Analysis:
 
 
• Proportion of participants with <math>\geq 0.5</math> point ACQ-5 score decrease from baseline (responder) at each week from Week 1 to Week 16.
 
• Proportion of St. George's Respiratory Questionnaire (SGRQ) responders (at least a 4 unit improvement from baseline) at Weeks 4, 8, 12 and 16.
 
	
Odds Ratio. The odds of being a responder on GSK3772847 compared to the odds of being a responder on placebo.

Change from Baseline Analysis:
 
 
• Change from baseline in pre-bronchodilator FEV1 at Weeks 2, 4, 6, 8, 10, 12, 14, 16.
 
• Change from baseline in fractional
 
	
Mean change from baseline

Endpoint	Summary Measure
exhaled nitric oxide (FeNO) at each week measured.	
Change from Baseline Analysis: 
 
• Change from baseline in ACQ-5 absolute score at each week from Week 1 to Week 16.
 
• Change from baseline in SGRQ total score at Weeks 4, 8, 12 and 16.
 
	Mean change from baseline

 
• Change from baseline in mean morning peak expiratory flow (PEF) and mean evening PEF for each four week period of the overall 16 week treatment period.
 
• Change from baseline in mean daytime asthma symptom score over each four weeks of the 16 week treatment period.
 
• Changes from baseline in night-time awakenings due to asthma symptoms requiring rescue medication use over each four weeks of the 16 week treatment period.
 
• Change from baseline in rescue medication use (albuterol/salbutamol): mean number of inhalations per day over each four weeks of the 16 week treatment period.
 
	Change from baseline (summary statistics only)

### 7.2.2. Population of Interest

The secondary efficacy analyses will be based on the modified Intent to Treat population, unless otherwise specified.

### 7.2.3. Strategy for Intercurrent (Post-Randomisation) Events

For components of Loss of Asthma Control see Section 7.1.4.

For SGRQ and ACQ Responders primary and secondary estimands as table below:

Intercurrent Event	Primary Estimand	Secondary Estimand
Treatment discontinuation due to AE/SAE (not related to loss of asthma control)	Set to missing.	
 
• If the AE/SAE was deemed related to IP then set as non-responder.
 
• If the AE/SAE was not deemed related to IP then set to missing.
 

Intercurrent Event	Primary Estimand	Secondary Estimand
Death	Set to missing.	
 
• If the death was deemed related to IP then set as non-responder.
 
• If the death was not deemed related to IP then set to missing.
 

Prohibited/ Concomitant medications that could impact patients' asthma control	Use data as is.	Set as non-responder.
Non-compliance with FP/SAL, FP or study titration	Use data as is.	Set as non-responder.

Note:
 
 
• Identification of whether an event (AE/SAE/Death) is considered related to IP will be identified using the investigator tick box collected on the eCRF.
 
• If the intercurrent event occurs after loss of asthma control then all information on loss of asthma control will be used.
 
• Prohibited/ concomitant medications will be identified as protocol deviations within the prohibited/ concomitant medications category and will have text that start with "LoAC"
 
• Non-compliance FP/SAL, FP or study titration will be identified as compliance <80%, compliance <math>\geq</math> 120% or not changing from FP/SAL or FP doses according to the predetermined schedule.
 
		

#### 7.2.4. Statistical Analyses / Methods

Details of the planned displays are provided in [Appendix 10: List of Data Displays](#) and will be based on GSK data standards and statistical principles.

Unless otherwise specified, endpoints / variables defined in Section 7.2.1 will be summarised using descriptive statistics, graphically presented (where appropriate) and listed.

##### 7.2.4.1. Statistical Methodology Specification

Endpoint / Variables

 
• Proportion of participants with a <math>\geq 0.5</math> point. ACQ-5 score increase from baseline.
 
• Proportion of participants who have pre-bronchodilator FEV1 decrease from baseline (measured at the end of Run-in) >7.5 %.
 
• Proportion of participants where inhaled corticosteroids (ICS) cannot be titrated in accordance with the pre-defined schedule.
 
• Proportion of participants who have a significant asthma exacerbation (requiring OCS and/or hospitalisation).
 
• Proportion of participants with a clinically significant asthma exacerbation or inability to titrate ICS according to the pre-defined schedule
 

Strategy for Intercurrent (Post-Randomisation) Events

Both primary and secondary estimands (Section 7.1.4) will be examined. It is important to assess both estimands as data is set to missing after withdrawal or loss of asthma control. This could produce biased estimands, as loss of control and therefore missing data is related to study treatment, and so the secondary estimand where missing data is set as non-responders must also be considered.

Model Specification

 
See Section 7.1.5.1.
 

Model Checking & Diagnostics

 
See Section 7.1.5.1
 

Model Results Presentation

 
See Section 7.1.5.1
 

Endpoint / Variables

 
Proportion of participants with <math>\geq 0.5</math> point ACQ-5 score decrease from baseline (responder) at each week from Week 1 to Week 16.
 
Proportion of St. George's Respiratory Questionnaire (SGRQ) responders (at least a 4 unit improvement from baseline) at Weeks 4, 8, 12 and 16.
 

Strategy for Intercurrent (Post-Randomisation) Events
Both primary and secondary estimands (Section 7.2.3 ) will be examined. It is important to assess both estimands as data is missing after withdrawal or loss of asthma control. This could produce biased estimands, as loss of control and therefore missing data is related to study treatment, and so the secondary estimand where missing data is set as non-responders must also be considered.
Model Specification

 
The proportion of participants who were responders will be analysed using logistic regression allowing for screening eosinophils strata.
 
A responder on ACQ-5 is defined as participants with a <math>\geq 0.5</math> point decrease from baseline whilst a responder on SGRQ is defined as a <math>\geq 4</math> point decrease from baseline.
 
This endpoint will be analysed using logistic regression. Treatment, eosinophil strata will be fixed effects.
 

Model Checking & Diagnostics

 
None
 

Model Results Presentation

 
The odds of being a responder (as defined above) on GSK3772947, Placebo and the odds ratio will be presented along with the 95% confidence intervals and p-value.
 

Endpoint / Variables

 
Time to loss of asthma control.
 

Strategy for Intercurrent (Post-Randomisation) Events

 
Both primary and secondary estimands (Section 7.1.4) will be examined. It is important to assess both estimands as data is missing after withdrawal or loss of asthma control. This could produce biased estimands, as loss of control and therefore missing data is related to study treatment, and so the secondary estimand where missing data is set as non-responders must also be considered.
 

Model Specification

 
Time to loss of asthma control will be analysed on the Modified Intent-to-Treat excluding GCP
 

non-compliant subjects (Loss of Control) population using Kaplan-Meier analysis (Proc lifetest). Within the Kaplan Meier plot participants will either be counted as an event or they will be censored.

Events:

- Participants who experience loss of asthma control during the study.

Censoring:

- Participants who discontinue investigational product for reasons other than loss of asthma control.
- Participants who successfully complete the 16 week treatment period will be censored at 113 days (16 weeks + 1 day).

Time to loss of asthma control = Date of loss of asthma control – Treatment start date + 1. If participants experience multiple reasons for loss of control then the earliest date will be used as described in Section [12.6.3](#).

### Model Checking & Diagnostics

- None

### Model Results Presentation

- Kaplan-Meier plots of the probability of a participant experiencing loss of asthma control by treatment will be produced.
- In addition, a summary table will be produced showing the probability of experiencing loss of asthma control after 4, 8, 12 and 16 weeks along with the median time (this will be NA if <50% of participants on a treatment lose control) to loss of asthma control on both treatment arms.

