## 2.5. Statistical Hypotheses

The primary null hypothesis ( $H_0$ ) for this study is that the ratio of the proportions of subjects with loss of asthma control from randomisation to Week 16 between GSK3772847 and placebo is unity.

$$H_0: \frac{\text{Proportion with loss of asthma control at Week 16 on GSK3772847}}{\text{Proportion with loss of asthma control at Week 16 on Placebo}} = 1$$

The alternative hypothesis ( $H_1$ ) for this study is that the ratio of the proportions of subjects with loss of asthma control from randomisation to Week 16 between GSK3772847 and placebo is not unity.

$$H_1: \frac{\text{Proportion with loss of asthma control at Week 16 on GSK3772847}}{\text{Proportion with loss of asthma control at Week 16 on Placebo}} \neq 1$$

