## 2.6. Sample Size Calculations

With 70 evaluable participants per arm and assuming the true proportion with loss of control on placebo is 44%, the smallest observed difference that would lead to rejection of the null hypothesis (minimum detectable effect) is 36% corresponding to a proportion with loss of control on GSK3772847 of 28%.

As detailed in Section 2.1, there was a typographical error in the protocol which meant that minimum detectable effect was incorrectly reported as 31%, this has been corrected above.

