### Model Results Presentation

Bayesian Method (Primary):

- The proportions of participants experience loss of asthma control on GSK3772847, Placebo and the ratio of GSK3772847/Placebo will be presented along with their 95% credible interval.

Frequentist Method (Supportive):

- The proportion of participants experiencing loss of asthma control on GSK3772847, Placebo and the odds ratio will be presented along with the 95% confidence intervals and p-value. This will be presented for all participants combined.

Fractional Polynomials (Exploratory Analysis):

- A plot of the relationship between the probability of experiencing loss of control on each treatment as well as the odds ratio versus continuous eosinophils will be produced.

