**7.2.4.1. Statistical Methodology Specification**

Endpoint / Variables

 
Time to loss of asthma control.
 

Strategy for Intercurrent (Post-Randomisation) Events

 
Both primary and secondary estimands (Section 7.1.4) will be examined. It is important to assess both estimands as data is missing after withdrawal or loss of asthma control. This could produce biased estimates, as loss of control and therefore missing data is related to study treatment, and so the secondary estimand where missing data is set as non-responders must also be considered.
 

Model Specification

 
Time to loss of asthma control will be analysed on the Modified Intent-to-Treat excluding GCP non-compliant subjects (Loss of Control) population using Kaplan-Meier analysis (Proc lifetest). Within the Kaplan Meier plot participants will either be counted as an event or they will be censored.
 
A log rank test will be performed to test for difference between the time to loss of asthma control on Placebo compared with GSK3772847
 
 
Primary Estimand:
 
 
Events: Participants who experience loss of asthma control during the study
 
Censoring: Participants who discontinue investigational product for reasons other than loss of asthma control will be censored at the date of early withdrawal from study treatment. Participants who successfully complete the 16 week treatment period will be censored at 113 days (16 weeks + 1 day).
 
 
Secondary Estimand:
 
 
Events: Participants who experience loss of asthma control during the study or who discontinue investigational product for reasons other than loss of asthma control (date of event will be set to date of early withdrawal from study treatment).
 
Censoring: Participants who successfully complete the 16 week treatment period will be censored at 113 days (16 weeks + 1 day).
 

Time to event/censoring = Date of event/censoring – Treatment start date + 1. If participants experience multiple reasons for loss of control then the earliest date will be used as described in Section 0.

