### Model Results Presentation

- Kaplan-Meier plots of the probability of a participant experiencing loss of asthma control by treatment will be produced.
- In addition, a summary table will be produced showing the probability of experiencing loss of asthma control by 4, 8, 12 and 16 weeks along with the median, upper and lower quartiles of time to loss of asthma control on both treatment arms (this will be NA if <50% of participants on a treatment lose control).

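### Time to loss of asthma control is compared between arms by a log-rank p-value alone, with no eosinophil stratum named and no effect estimate or confidence interval

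*SAP*

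**What the plan says.** The SAP file contains the amended RAP followed by the December 2018 RAP that it replaces. The amended RAP governs.

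Its Section 7.2.4.1 analyses time to loss of control by Kaplan-Meier in the mITT (Loss of Control) population and adds one comparison: "A log rank test will be performed to test for difference between the time to loss of asthma control on Placebo compared with GSK3772847". Under the primary estimand, participants who stop study treatment for other reasons are censored at withdrawal. Under the secondary estimand they count as events on that date. Completers are censored at Day 113.

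The results paragraph says "In addition, a summary table will be produced showing the probability of experiencing loss of asthma control by 4, 8, 12 and 16 weeks", together with each arm's median and quartiles, shown as NA when fewer than half of an arm lose control. Section 7.2.1 adds each arm's mean. Tables 2.12 and 2.13 hold this for the two estimands, and Figures 2.9 and 2.10 are the Kaplan-Meier plots.

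The December 2018 text has nearly the same sentence, "In addition, a summary table will be produced showing the probability of experiencing loss of asthma control after 4, 8, 12 and 16 weeks", with a median in its table and no log-rank test. It is background only.

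Section 5.4.1 states that the screening eosinophil stratum enters both primary and secondary analyses. Section 2.6 supplies the only event rates: "With 70 evaluable participants per arm and assuming the true proportion with loss of control on placebo is 44" per cent, and the "minimum detectable effect) is 36% corresponding to a proportion with loss of control on GSK3772847 of 28" per cent.

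**The concern.** The secondary efficacy objective is a comparison with placebo. After the amendment, the loss-of-control components, the ACQ-5 and SGRQ endpoints, PEF, symptoms and rescue use are summarised only, and FEV1, FeNO and eosinophils are modelled only to Week 4. Time to loss of control is therefore the one secondary efficacy endpoint tested between arms through Week 16, across the whole inhaled-steroid taper.

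For that endpoint a reader would learn whether the p-value is small, but not how large the effect is or how precisely it is known. Section 7.2.3 says both estimands matter because of possible bias. Within Tables 2.12 and 2.13, however, only two p-values and two sets of per-arm figures could be compared. The test as written also leaves out the stratification factor that Section 5.4.1 promises.

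**Working it through.** **1. Between-arm results planned for each analysed efficacy endpoint (current RAP).**
- Loss of control, Weeks 0-16 and 0-6: posterior ratio with 95% credible interval; odds ratio, which "will be presented along with the 95% confidence intervals and p-value".
- FEV1 to Week 4: difference with 95% CI and p-value.
- FeNO and eosinophils to Week 4: ratios with 95% CI and p-value.
- Time to loss of control: log-rank p-value only.

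**2. The plan's own figure.** Inputs from Section 2.6: n = 70 per arm, 44% and 28%. The alternative in Section 2.5 is two-sided (the ratio "between GSK3772847 and placebo is not unity"). Alpha is not stated there; 0.05 is inferred from the 95% intervals.
- Pooled z = 0.16 / sqrt(2 × 0.36 × 0.64 / 70) = 1.97, just past 1.96.
- Relative reduction = 0.16 / 0.44 = 36%.

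The figure reproduces. It also confirms that 28% is the observed rate at which the test just rejects, not an assumed true rate on active. What follows uses it only as an illustration.

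**3. Which per-arm quantiles can be expected by Day 113, primary estimand?** No censoring is assumed.
- Median (needs 50%): 44% and 28% both fall short. P(Bin(70, 0.44) ≥ 35) = 0.186 and P(Bin(70, 0.28) ≥ 35) = 0.00008. The placebo median thus has about a 19% chance of being reached; the active median has almost none if the true rate were 28%.
- Upper quartile (needs 75%): not expected in either arm.
- Lower quartile (needs 25%, i.e. 18 of 70): both rates exceed 25%. P(Bin(70, 0.44) ≥ 18) is above 0.999 and P(Bin(70, 0.28) ≥ 18) = 0.71, so it is estimable in expectation in both arms. Read literally, though, the NA rule in the results paragraph also covers the quartiles and would blank it whenever fewer than half lose control.

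**4. Secondary estimand.** Other withdrawals count as events. With a fraction w of those keeping control withdrawing, an arm reaches 50% when:
- placebo: 0.44 + 0.56w = 0.50, w = 0.06 / 0.56 = 10.7%;
- active: 0.28 + 0.72w = 0.50, w = 0.22 / 0.72 = 30.6%.

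The SAP gives no withdrawal rate. Over an assumed 0 to 20%, the event proportion runs from 44% to 55% on placebo and from 28% to 42% on active.

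**5. What an effect estimate would look like at 44% against 28%, no censoring.**
- Events: 70 × 0.44 = 30.8 and 70 × 0.28 = 19.6.
- Hazard ratio, proportional hazards assumed: ln(0.72) / ln(0.56) = 0.57. SE of the log = sqrt(1/19.6 + 1/30.8) = 0.289, so the 95% CI is about 0.32 to 1.00. With SE = 2 / sqrt(50.4) it is 0.33 to 0.98.
- Week 16 difference: 0.16, SE = sqrt((0.44 × 0.56 + 0.28 × 0.72) / 70) = 0.080, 95% CI 0.3 to 31.7 points.

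**The case against.** Kaplan-Meier with a log-rank test is a conventional choice for a secondary endpoint without multiplicity control in a Phase IIa trial. The plan already reports effect sizes for the same event in the same population: Tables 2.4 to 2.11 give ratios and odds ratios with intervals for Weeks 0-16 and 0-6 under both estimands, and Section 2.1 says the Weeks 0-6 endpoint was added to support this analysis. Differences at Weeks 4, 8, 12 and 16 can be found by subtracting the per-arm probabilities. Background therapy is stepped down from Week 2 to Week 10, so proportional hazards is doubtful and leaving out a Cox model is defensible. The table shell (EFF_T05) is only available on request, so the full layout cannot be seen.

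Most of this stands, and it limits the consequence. It does not supply the missing estimate. Subtracting two per-arm probabilities gives no interval. Nor is the binary analysis the same quantity: its primary estimand excludes participants with AE discontinuation, death or missing data (Section 7.1.4), whereas the time-to-event analysis keeps those who stop for other reasons and censors them at withdrawal. The doubt about proportional hazards bears on which measure to choose, not on whether to give one. A table shell cannot stand in for a measure that Sections 7.2.1 and 7.2.4.1 do not specify.

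**Conclusion.** The point holds as a cheap improvement, not as an error in the plan. In the current RAP the time-to-event analysis yields one between-arm result per estimand, a log-rank p-value with no eosinophil stratum named, and no effect size or precision.

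Three stronger readings are tempting, and the document does not support them:
- That the median cannot be reached in either arm. It is merely not expected under the primary estimand. Placebo has about a 19% chance of reaching it, and under the secondary estimand it is reached once about 11% of those keeping control withdraw. The lower quartile and the Kaplan-Meier probabilities at four time points remain informative.
- That the plan assumes a true rate of 28% on active. Section 2.6 defines it as the rejection boundary, so the near-zero chance for the active median and the hazard ratio of 0.57 describe one scenario.
- That the trial would give no effect size for loss of control. The binary analyses do so, with intervals, under both estimands.

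The illustrative sizes (hazard ratio about 0.57, 95% CI about 0.32 to 1.00; difference 16 points, about 0 to 32) assume 70 evaluable per arm and no censoring. The hazard ratio also assumes proportional hazards.

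**What to change.** In Section 7.2.4.1 and Tables 2.12 and 2.13 of the current RAP:
- stratify the log-rank test by screening eosinophil stratum, in line with Section 5.4.1;
- add the between-arm difference in Week 16 Kaplan-Meier probability with a 95% CI from Greenwood variances;
- add the GSK3772847/placebo hazard ratio with a 95% CI from a Cox model that includes the eosinophil stratum.

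Do this for both estimands, and list the two measures in Section 7.2.1. The same edit could state the NA threshold separately for each quantile (25%, 50% and 75%).

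The cost is SAP wording, two extended tables and a small amount of programming on the existing time-to-event dataset; no new data are needed. The downside is that the hazard ratio assumes proportional hazards, which may fail through the steroid taper. The Week 16 difference does not need that assumption and can be read alongside it.
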